## 1.0 PROTOCOL SUMMARY AND/OR SCHEMA

This is a multi-center, open-label, phase 2 trial testing the efficacy and safety of 2 interventions that target rash during PI3K inhibitor therapy in postmenopausal women and men with histologically-confirmed, hormone receptor (HR)-positive, HER2-negative, PIK3CA mutant metastatic breast cancer (MBC). A total of 63 patients will be enrolled into one arm: benralizumab 30mg in combination with standard of care (SOC) endocrine therapy (fulvestrant or AIs or aromatase inhibitors (AIs)) and PI3K inhibition (alpelisib). A total of 43 patients will be enrolled at MSKCC and a total of 20 patients will be enrolled at the participating external institutions (10 patients at Stanford University and 10 patients at Dana Farber Cancer Institute). The primary endpoint is the proportion of patients with grade  $\leq 1$  rash rate at 4 weeks.

**Patient Population:** The primary study population will be postmenopausal women and men with histologically-confirmed, HR-positive, HER2-negative, *PIK3CA* mutant MBC who have received no more than 2 lines of endocrine-based therapy in the metastatic setting.

**Design:** A multi-center, open-label, phase 2 trial testing the efficacy and safety of one interventions (one anti IL-5 receptor antibody and one antihistamine) that target the maculopapular rash during PI3K inhibitor therapy in patients with HR-positive, HER2-negative, *PIK3CA* mutant MBC receiving first or second line therapy. Study participants (n=112) will enrolled to one arm: benralizumab (anti-IL5ra) in combination with SOC endocrine therapy (fulvestrant or AIs) and PI3K inhibition (alpelisib). The primary endpoint is the grade  $\leq 1$  rash rate at 4 weeks. The study size is determined to compare the grade  $\leq 1$  rash rate at four weeks with historical controls. It has been reported that approximately 34% of patients receiving alpelisib will develop  $\geq$  grade 2 rash within the first 30 days. The corollary is that 66% of historical controls will have grade  $\leq 1$  rash within the first 30 days. An increase in rash control to approximately 88% is deemed to be clinically meaningful with the investigational agent under investigation (IL5r antibody). A sample size of 57 patients per group will achieve an 80% power to detect an odds ratio of 4.0 with respect to the primary endpoint. The proportion in the experimental group is assumed to be 0.66 under the null

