hypothesis and 0.88 under the alternative hypothesis. The proportion is 0.66. If it is assumed that 10% of patients will withdraw consent or be lost to follow up, then 63 patients will need to be enrolled into this trial.

**Treatment Plan:** All participants will receive SOC endocrine therapy (fulvestrant or AIs) and PI3K inhibition (alpelisib). Participants will receive benralizumab 30mg subcutaneously on day -1. All participants will be monitored at regular visits for the duration of the trial. After 4 weeks, patients will be followed for safety at 90 days and disease progression for 1 year.

**Estimated Time to Completion:** 1 years.

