### **7.2 Randomization**

No randomization will occur in this study. After eligibility is established and immediately after consent is obtained, patients will be registered in the Clinical Trials Management System (CTMS).

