## 14.0 BIOSTATISTICS

### Sample Size

This will be a single arm trial. The target sample size is intended to test the hypothesis that benralizumab reduces the frequency of grade  $\geq$  grade 2 rash at 4 weeks relative to the historical controls in patients receiving alpelisib. The primary endpoint in the current study will be the proportion of patients to achieve a rash grade of 1 or less. It has been reported that approximately 34% of patients receiving alpelisib will develop  $\geq$  grade 2 rash within the first 30 days. An increase in rash control to approximately 88% is deemed to be clinically meaningful with the investigational agent. Sample sizes of 57 patients achieves an 80% power to detect a difference based on a two sample proportions test. Due to potential attrition during the course of the study, the sample size will be increased by 10%. The resultant sample size will be 63 patients.

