### General Statistical Plan

There will be one analysis population for the current study. The modified intent to treat (ITT) population will be all patients regardless of treatment compliance for whom investigators were able to obtain a 4-week efficacy assessment. The safety population will be patients who received at least one dose of study drug or the standard of care, regardless of any efficacy assessments. All efficacy analyses will be based on the modified ITT population. Patient, clinical and safety data as well as primary, secondary and exploratory endpoints will initially be presented descriptively as means, medians, or proportions with appropriate measures of variance (i.e. range, SD, 95%CI). The primary endpoint,  $\geq$  grade 2 rash versus  $<$  grade 2 rash will be evaluated using generalized linear models (GLIM), with a logit link function and a Bernoulli distribution. A group\*time interaction will be included to assess the difference in the outcome measure at the specific study time points. Differences in the frequency of grade 0/1 rash overall all study visits (days 14, 28 and 90) will be assessed using mixed models for repeated measures as a secondary analysis.

The total number of dose reductions and delays between study groups over the trial period will be compared using Poisson regression analysis. The absolute difference in the FACT-B and PRO-CTCAE scores from day 1 to 14 and 28 between groups will be also be evaluated using repeated measures mixed models. The cumulative dose of corticosteroid use between

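### The 80% power stated for 57 patients belongs to a two-group test, not to this single-arm trial, and the primary test has no alpha, no success rule and no second group

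*Combined protocol and SAP*

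**What the plan says.** **Design.** Section 14.0, Sample Size, opens with "This will be a single arm trial", and section 7.2 says "No randomization will occur in this study".

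**Sizing.** The same Sample Size paragraph states "Sample sizes of 57 patients achieves an 80% power to detect a difference based on a two sample proportions test". Section 1.0 puts it as "A sample size of 57 patients per group will achieve an 80% power to detect an odds ratio of 4.0". Section 1.0 then gives a hypothesis about one group: "The proportion in the experimental group is assumed to be 0.66 under the null", continuing "hypothesis and 0.88 under the alternative hypothesis". A further short sentence repeats 0.66 without naming a group.

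**Comparator.** Historical controls are named in sections 1.0, 2.0 and 14.0. The 66% is the complement of a reported 34% of alpelisib patients with grade 2 or worse rash in the first 30 days. No source, number of controls or assessment schedule is given for it.

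**Analysis.** The General Statistical Plan uses a logistic model in which a group-by-time "interaction will be included to assess the difference in the outcome measure at the specific study time points". For secondary outcomes it says, for example, "The total number of dose reductions and delays between study groups over the trial period will be compared using Poisson regression analysis", and lists Wilcoxon, log-rank, Cox and chi-square methods. No section states an alpha, its sidedness or the number of successes that would make the trial positive.

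**Endpoint.** Section 13.1 defines patient success as grade 1 or less at 4 weeks. Section 11.0 places that visit at day 28 with a 7-day window either way. A parenthesis in section 12.0 refers to a rash event before 4 weeks.

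**The concern.** The design has one group, while the sample-size statement and the primary model have two. If the quoted power belongs to a different test from the one that will be run, it does not describe this trial. If the primary model cannot be fitted to the enrolled patients, the test will have to be chosen later. The trial is open-label and section 14.0 sends data out for analysis every quarter, so that choice could be made with results in view.

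The benchmark raises a related question. A rash that appears early and clears by day 28 is a failure in a rate of rash developing within 30 days, but a success if only the grade at the 4-week visit counts. A mismatch of that kind would favour the drug.

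**Working it through.** **Inputs.** p0 = 0.66 and p1 = 0.88 (section 1.0); n = 57 and 80% power (sections 1.0 and 14.0). Alpha is not in the documents. Two-sided 0.05 is inferred below because it reproduces 57; one-sided 0.025 and 0.05 are assumed for the one-sample test.

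**1. Reproducing the plan's figure (1:1, two-sample, pooled z, two-sided 0.05).** The mean rate is 0.77.

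- n per group = [1.960 × √(2 × 0.77 × 0.23) + 0.842 × √(0.66 × 0.34 + 0.88 × 0.12)]² / 0.22² = [1.166 + 0.483]² / 0.0484 ≈ 56.2, so 57 per group.
- Power at 57 per group = Φ[(0.22 × √57 − 1.166) / 0.574] = Φ(0.861) = 80.5%. At 56 per group it is 79.8%.

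The stated 57 and 80% are therefore per-group figures for a trial of 2 × 57 = 114 patients.

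**2. One arm against a fixed 0.66.** The normal approximation for 80% power gives n = [(1.960 × √0.2244 + 0.842 × √0.1056) / 0.22]² ≈ 29.8, so 30 patients (23 at one-sided 0.05). No one-sample version tried gives 57. Exact binomial results at a true rate of 0.88:

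| n | One-sided alpha (assumed) | Success if at least | Actual alpha | Power |
|---|---|---|---|---|
| 57 | 0.025 | 45 | 0.024 | 98.4% |
| 57 | 0.05 | 44 | 0.047 | 99.4% |
| 63 | 0.025 | 50 | 0.015 | 98.4% |
| 63 | 0.05 | 49 | 0.030 | 99.3% |

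With 57 patients, 80% power is reached at a true rate of about 0.823 (one-sided 0.025) or 0.807 (one-sided 0.05).

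**3. One arm against a sampled cohort of size m.** The documents do not give m, so these are illustrations. Power = Φ[(0.22 − 1.960 × √(p̄(1 − p̄)(1/57 + 1/m))) / √(0.1056/57 + 0.2244/m)], where p̄ is the size-weighted mean rate.

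| m | 30 | 57 | 100 | 200 |
|---|---|---|---|---|
| Power, two-sided 0.05 | 68% | 81% | 89% | 94% |

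The stated 80% fits only a cohort of about 57.

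**4. The primary model.** Take the three visits that section 14.0 lists (days 14, 28 and 90). Intercept, group, two visit terms and two interaction terms make six columns. When every patient is in the same group, the group column equals the intercept and the interaction columns equal the visit columns. The rank is 3 of 6, so neither the group effect nor the interaction can be estimated without outside data.

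**5. Endpoint basis (illustration only).** If the comparable untreated rate at the day-28 visit were 70%, a figure the plan does not give, then 45 or more of 57 would be reached with no drug effect in 8.9% of trials, against 2.4% at 66%.

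**6. Smaller inconsistencies.** The odds ratio is (0.88/0.12) / (0.66/0.34) = 3.78, not 4.0. Section 1.0 gives both 112 and 63 participants. Section 7.0 calls the 63 evaluable, whereas sections 1.0 and 14.0 reach 63 by adding about 10% to 57 for attrition (57 × 1.1 = 62.7).

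**The case against.** The strongest reply is that much of this is leftover text. The documents still refer to an antihistamine intervention in section 1.0, section 13.2, the novelty paragraphs of section 13.3 and section 14.0, and 112 is 2 × 56. The per-group wording, the two-sample test and the group-by-time term may all come from a dropped second arm. That is plausible and would explain the mismatch, but the current text still needs a test that fits one arm.

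Several stronger readings are tempting and are not supported:

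- *No comparator is stated.* Historical controls and a 66% rate are named. What is missing is the source, the size, and whether the rate is fixed or sampled.
- *The analysis plan shows that a patient-level historical cohort will be used.* The General Statistical Plan never mentions historical data, and its groups may be the two former arms. A chi-square test needs only counts, and a group-only Poisson comparison needs only totals and exposure. The secondary objectives in sections 2.0 and 13.2 do ask for historical comparison, so the intention stays open.
- *The trial is too small.* Against a fixed 66% it has more power than stated. Power falls below 80% only with a cohort smaller than about 57, and no document suggests one.
- *The fixed and cohort readings would often give opposite verdicts.* At a true rate of 0.88, with 57 controls and two-sided 0.05, they differ in 12% of trials if the cohort shows 38/57 but in 5.8% if it shows 37/57. Such a figure is too fragile to rely on.
- *The error rate is inflated by the endpoint.* The primary objective speaks of incidence, and a 4-week rate can be read cumulatively, which would match the 30-day benchmark. No resolution time or day-28 rate is given, so the size of any bias is unknown.

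**Conclusion.** The point stands as a mismatch between design, sizing and primary analysis. The stated 80% is the power of a 1:1 two-group trial with 57 per group. For the one-sample hypothesis in section 1.0 the power is about 98% (one-sided 0.025) or 99% (one-sided 0.05); for a sampled cohort it is undetermined. The primary model cannot be run on the enrolled patients alone, and the rule for a positive trial is absent. This should be fixed before outcomes are analysed.

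The two-group reproduction rests on an inferred two-sided 0.05, and the one-sample figures on assumed alphas. The cohort sizes and the 70% day-28 rate are illustrations. The endpoint ambiguity is a separate wording defect: its direction would favour the drug if the visit-grade reading applies, and its size cannot be derived from the documents.

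**What to change.** 1. State whether 66% is a fixed benchmark or a sampled cohort. If fixed, as section 1.0 reads, replace the two-sample sizing statement and the group-by-time model with a one-sample exact binomial test of H0: p ≤ 0.66. Give alpha, a success count for the evaluable n, an exact confidence interval and the resulting power. For n = 57 and one-sided 0.025 that is at least 45/57, with about 98% power at 0.88 and 80% at about 0.82. Report the between-group secondary analyses as single-arm estimates with confidence intervals.
2. If a cohort is used, name it, give its size and rash-assessment times, and recompute power for that size.
3. Put endpoint and benchmark on one basis and align sections 12.0 and 13.1. One option is any grade 2 or worse rash through 4 weeks, which fits the incidence objective and the 30-day source. The other is grade at the day-28 visit, with a matching historical rate.
4. Reconcile 112 with 63, evaluable with enrolled, and odds ratio 4.0 with 3.78, and remove the antihistamine remnants.

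**Cost.** Wording in sections 1.0, 7.0, 12.0, 13.1 to 13.3 and 14.0. No extra patients under the fixed 66% reading. A small cohort or a higher null rate would lower power and must be checked: with a null of 0.70 and one-sided 0.025, the count becomes 47/57 and power at 0.88 is 92.6%.

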### General Statistical Plan

There will be one analysis population for the current study. The modified intent to treat (ITT) population will be all patients regardless of treatment compliance for whom investigators were able to obtain a 4-week efficacy assessment. The safety population will be patients who received at least one dose of study drug or the standard of care, regardless of any efficacy assessments. All efficacy analyses will be based on the modified ITT population. Patient, clinical and safety data as well as primary, secondary and exploratory endpoints will initially be presented descriptively as means, medians, or proportions with appropriate measures of variance (i.e. range, SD, 95%CI). The primary endpoint,  $\geq$  grade 2 rash versus  $<$  grade 2 rash will be evaluated using generalized linear models (GLIM), with a logit link function and a Bernoulli distribution. A group\*time interaction will be included to assess the difference in the outcome measure at the specific study time points. Differences in the frequency of grade 0/1 rash overall all study visits (days 14, 28 and 90) will be assessed using mixed models for repeated measures as a secondary analysis.

The total number of dose reductions and delays between study groups over the trial period will be compared using Poisson regression analysis. The absolute difference in the FACT-B and PRO-CTCAE scores from day 1 to 14 and 28 between groups will be also be evaluated using repeated measures mixed models. The cumulative dose of corticosteroid use between

the Benralizumab group over the study period will be compared using the Wilcoxon Rank Sum test. Time to the development of grade 1 or 2 rash will be evaluated using Kaplan-Meier time to event curves and assessed using the log rank test and Cox proportional hazards regression analysis. The Yates corrected chi square test will be used to compare the frequency of non-skin alpelisib related adverse events between groups, as well as 6 and 12 month ORR and PFS. Differences between the Benralizumab group on IL-5 inhibition and antihistamines and non-skin alpelisib related adverse events will be evaluated using linear mixed models. Changes in inflammatory biomarkers in skin and related to rash and all other exploratory endpoints will only be evaluated graphically with descriptive statistics. Given the exploratory nature of the current trial, there will be no adjustments for multiplicity. All the statistical analyses will be performed using SAS® Version 9.4 or higher. De-identified data will be shared via MSK secured e-mail quarterly to Augmentium Pharma Consulting for statistical analysis.

Patients may be removed from the study for various reasons as outlined in section 12.0 of the protocol. Descriptive statistics will be reported separately for patients removed from the study, including a summary of reasons for removal, their median duration in the study and range, median, range, and the distribution of rash grades at all follow-up times prior to their removal from the study.

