Previous analyses suggests that histamine producing cells and eosinophils have some role in alpelisib-related rash. All patients receiving alpelisib have a trend towards increased eosinophils, with a more pronounced effect in patients with rash. Interestingly, pre-treatment absolute eosinophil count may be lower in patients who develop rash. We also found that patients developing rash had a statistically significant increase in eosinophils after 2 weeks of

receiving alpelisib ( $p < 0.05$ ) (below, left). This has also been demonstrated in phase 1

study of alpelisib in combination with fulvestrant or Als (below, right). Prospective analyses and anecdotal experience at MSK with over 100 patients has revealed that 90% of rash develops within the first 4 weeks. Indeed, the median time to onset of grade 3-4 rash was 13 days in the pivotal SOLAR-1 trial.

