### Rash

Table 2. Dose modification and management for rash.

Grade	Recommendation
Grade 1  Macules/papules covering <10% BSA with or without symptoms (e.g., pruritus, burning, tightness)	No dose adjustment required.  OTC moisturizers and sun protection
Grade 2  Macules/papules covering 10 - 30% BSA with or without symptoms (e.g., pruritus, burning, tightness); limiting instrumental ADL; rash covering > 30% BSA with or without mild symptoms	No dose adjustment required.  OTC moisturizers and sun protection
Grade 3 Macules/papules covering >30% BSA with moderate or severe symptoms; limiting self care ADL	Interrupt alpelisib.  Prednisone 50mg a day over 10 days (with pneumocystis prophylaxis and PPI). Restart alpelisib as per package insert.
Grade 4 (SJS/TEN)  Life-threatening consequences; urgent intervention indicated	Permanently discontinue alpelisib, consult with dermatologist

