## 11.0 EVALUATION DURING TREATMENT/INTERVENTION

Patients will be seen on day -1 of treatment initiation, day 14, and day 28 with a +/- 7 day window. Each evaluation will consist of the following:

- History and dermatologic examination with standardized photography, ECOG performance status.
- Recording of the adverse events
- Labs, skin tape strips per Table 8

Patients will be assessed radiographically per standard of care.

The PRO-CTCAE, FACT, and allergy questionnaire (Block 2014 FFQ) will be administered at baseline and every 2 weeks (Appendices 2- 4). The allergy questionnaire will be administered at baseline.

All visits will be conducted within the Breast Medicine Service. Any patients with active rash at the time of their study visit should also be evaluated for the rash by the dermatology service for CTCAE grading, photography, and management. If a patient does not have a rash, baseline photography will not be performed; documentation will reflect the absence of a baseline rash.

Table 9 Study Procedures.

Study Procedures	Screening with 14 days of D - 1	Day - 1 to - 7	Day 1 Alpelisib initiation	Day 14±7	Day 28±7	Day 90 (Safety Visit)	Day 365 (Follow Up)
Informed consent	X						
Demographics	X						
Medical history	X						
ECOG	X			X	X		
Skin exam	X			X	X	X	
Vital signs	X			X	X	X	
Comeds	X			X	X	X	
Study Questionnaires	X			X	X	X	
AE evaluation	X			X	X	X	
Skin tape strips	X			X	X		
CBC with Differential/chemistry	X			X	X		
IgE (serum total)	X			X	X		
Allergy Panel	X						
Hyperglycemia panel	X			X	X		
Skin biopsy				X 	X 		
Cytokine panel	X			X	X		
Benralizumab injection		X					
Alpelisib			Once a day by mouth				
Chart Review							X

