## 12.0 CRITERIA FOR REMOVAL FROM STUDY

- 1) > 2 consecutive weeks of a delay in treatment due to toxicities
- 2) Progressive disease (breast cancer)
- 3) Unacceptable toxicity
- 4) Intercurrent, non-cancer related illness that prevents continuation of protocol therapy or follow-up
- 5) Major protocol violation that would render the patient inevaluable for efficacy
- 6) Repeated non-compliance by the patient with protocol requirements
- 7) Changes in the patient's condition or study intervention related toxicity such that, in the opinion of the investigator, continued participation in the protocol would compromise patient well-being
- 8) Withdrawal of patient's consent for personal reasons
- 9) Death

We do not expect any of the above criteria to occur with high frequency as the 4 week PFS for this population is over 90%. All participants for whom we are able to obtain the 4 week primary endpoint (had rash event prior to 4 weeks) will be considered evaluable for the primary rash endpoint under the intention-to-treat (ITT) approach.

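### Read literally, Section 14.0 drops a patient with observed grade 2+ rash who leaves before a week-4 assessment; Section 12.0 calls such a patient evaluable and the 66% benchmark counts the rash as a failure

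*Combined protocol and SAP*

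**What the plan says.** - **Analysis set.** Section 14.0 (General Statistical Plan) defines a modified ITT population of all patients "regardless of treatment compliance for whom investigators were able to obtain a 4-week efficacy assessment", and uses it for all efficacy analyses. It has no clause for a patient whose rash was seen earlier. The same section defines the primary outcome by a cut at grade 2.
- **Evaluability.** Section 12.0, speaking of participants whose 4-week endpoint can be obtained, adds a parenthesis: "had rash event prior to 4 weeks) will be considered evaluable for the primary rash endpoint under the intention-to-treat (ITT) approach". No grade is attached to the event, and the text does not say that it scores as a failure.
- **Benchmark.** Section 14.0 (Sample Size): "It has been reported that approximately 34% of patients receiving alpelisib will develop" grade 2 or worse rash in the first 30 days. Section 1.0 turns this round: "The corollary is that 66% of historical controls will have grade" 1 or lower over the same period. The null rate is therefore 66%.
- **Removal.** Section 12.0 lists more than "2 consecutive weeks of a delay in treatment due to toxicities", and unacceptable toxicity with no time limit. Neither 12.0 nor Table 9 lists a visit at removal.
- **Removed patients.** Section 14.0 summarises them separately and descriptively, including their reasons for removal and their rash grades up to that point. It does not say how they enter the primary analysis.

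**The concern.** The two sections use different labels (ITT, modified ITT) and different conditions (a rash event, a week-4 assessment). Two analysts working from the same data could therefore use different denominators for the primary result.

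The patient at issue has grade 2+ rash and leaves before a week-4 assessment. Such a patient is a failure in the source of the 66%, evaluable under 12.0, and absent under a literal 14.0. The trial has no concurrent control in which the same exclusion could balance out. Removing only rash failures raises the observed success rate against a fixed 66%, so any bias favours the drug.

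**Working it through.** **The plan's own sample size.** For 0.66 against 0.88 with 80% power (two-sided 0.05 assumed, because alpha is not stated), the pooled two-sample formula is

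n = [1.96·√(2·0.77·0.23) + 0.8416·√(0.66·0.34 + 0.88·0.12)]² / 0.22² = (1.166 + 0.483)² / 0.0484 ≈ 56.2, so 57 per group.

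Then 57 × 1.10 = 62.7, so 63. Both planned figures reproduce and are not in dispute here.

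**Who can be lost.**

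1. Stopping alpelisib does not remove a patient from the set, because 14.0 disregards compliance. Only leaving without a week-4 assessment matters.
2. For grade 2 rash, Table 2 states "No dose adjustment required". Grade 3 interrupts alpelisib and grade 4 stops it.
3. Section 11.0 sets visits at "day 14, and day 28 with a +/- 7 day window", so the week-4 window opens at day 28 − 7 = 21.
4. Section 3.4 reports that "the median time to onset of grade 3-4 rash was 13 days in the pivotal SOLAR-1 trial". A delay of more than 14 days that starts on day 13 meets the removal rule at about day 27–28, inside the window. For the rule to be met before day 21, the delay must start by about day 6.
5. Unacceptable toxicity, investigator judgement and withdrawal of consent can act at any time. The documents give no number for any of them.

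**Size, as an illustration.** The exact one-sample test, the one-sided 0.025 and every loss rate q are assumptions. Section 14.0 itself names a two-sample proportions test for sample size and a logit model for analysis.

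- Successes X ~ Bin(63, 0.66). Failures lost K ~ Bin(63 − X, q). The analysed number is n = 63 − K.
- Reject if X ≥ c(n), the smallest c with P(Bin(n, 0.66) ≥ c) ≤ 0.025. This gives c(63) = 50, c(62) = 49, c(61) = 48, c(60) = 48, c(59) = 47.
- Expected number lost = 63 × 0.34 × q.
- Apparent success rate = 0.66 / [0.66 + 0.34(1 − q)].

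| Failures lost (q) | Expected patients lost | Apparent rate when the truth is 66% | False-positive rate | Same rate of loss in successes too |
|---|---|---|---|---|
| 0% | 0 | 66.0% | 1.5% | – |
| 3% | 0.6 | 66.7% | 2.2% | 1.8% |
| 5% | 1.1 | 67.1% | 2.7% | 1.8% |
| 10% | 2.1 | 68.3% | 4.2% | 1.8% |

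The last column shows what loss unrelated to rash would do. The part due to losing only failures is therefore about 0.4, 0.9 and 2.4 percentage points. The assumed 2.5% is passed at a loss of about 4–4.5% of failures. If exactly two failures were always lost, the rate would be P(Bin(63, 0.66) ≥ 48) = 5.5%.

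At a true 88%, losing 10% of failures means 63 × 0.12 × 0.10 ≈ 0.8 patients. The apparent rate becomes 0.88 / (0.88 + 0.12 × 0.90) = 89.1%.

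**The case against.** The strongest reply is that the sections do not conflict. Section 14.0 asks whether a 4-week assessment was obtained, and the parenthesis in 12.0 may say when the 4-week endpoint counts as obtained. Section 14.0 also refers to 12.0 for removals. On that reading every early failure is kept and the bias is zero. This reading is available and may be what was intended. What stands is that 14.0 does not state it, that the event in 12.0 has no grade, and that patients who leave without grade 2+ rash have no rule.

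The second reply is that few patients are exposed, for the reasons set out in the working, and that 12.0 expects removals to be infrequent. That is accepted. A dropped failure would also show in the summary of removed patients, so a reader could restore it. The primary result would still depend on which section was followed.

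The third reply is that the endpoint is worded as a rate at 4 weeks. Read as a point in time, an early leaver is missing rather than failed, because the rash might have resolved. This is a fair limit. The point takes the first-30-days reading that the benchmark uses.

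A reader might infer more: that the plan certainly discards its failures, or that the whole 10% attrition allowance could be rash failures. The second would turn 42/63 = 66.7% into 42/57 = 73.7%. The documents do not support either. The first ignores the reconciling reading. The second reassigns an allowance that Section 1.0 describes as withdrawal of consent and loss to follow-up.

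**Conclusion.** The point holds in a limited form and should be fixed. Sections 12.0 and 14.0 can be followed to different primary denominators, and the literal 14.0 rule omits failures that the benchmark counts. The direction of any bias is clear: it favours benralizumab. Its size is not known and is probably small. Under the assumed test, losing 5% or 10% of failures takes the false-positive rate from 1.5% to 2.7% or 4.2%. At the design alternative the observed rate would hardly move.

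The conclusion assumes that the endpoint is read as the benchmark is, over the first 30 days, and that leaving is related to rash. There is no bias if the 12.0 rule governs every early failure, or if leaving is unrelated to rash. How the benchmark source handled its own early leavers is not shown.

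**What to change.** Make 12.0 and 14.0 state the same rule:

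1. The primary analysis set is every treated patient with a week-4 assessment or an earlier grade 2+ rash.
2. A patient with an earlier grade 2+ rash counts as a failure, whether or not a week-4 assessment exists.
3. Patients who leave without grade 2+ rash and without a week-4 assessment are reported by number and reason, with missing=failure as a sensitivity analysis.

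Rule 2 scores a rash that resolves by week 4 as the benchmark does. If the sponsor intends a point-in-time endpoint, its match to the benchmark is a separate question, and the leavers still need a stated rule.

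The cost is a wording amendment and a slightly lower reported success rate. No new data or visits are needed, because skin examinations and adverse events are already recorded at days 14 and 28. A rash that arises after the last visit and is never graded falls under the sensitivity analysis.

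Missing=failure should stay a sensitivity analysis because it costs power when many leave rash-free. At 88% among those observed and a cut-off of 50/63, P(Bin(63 − m, 0.88) ≥ 50) is 98% with m = 0 missing, 94% with 2 and 62% with 6.
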